5. *Comparison intervention practitioner expertise.* Pragmatic trials do not standardize which and how practitioners implement the intervention. In this case, we will cluster-randomize all of the PCPs in our practice to the intervention and will not standardize who or how they will implement the communication strategies. Score = 5.
6. *Follow-up intensity.* Purely pragmatic trials do not have any formal follow-up visits of the individuals and use passive administrative databases to detect outcomes. Given the importance of patient-reported outcomes in this study, we will use a combination of passive and active follow-up methods to ascertain outcomes; these have low respondent burden and only require the completion of short questionnaires. Score = 4.
7. *Primary trial outcome.* Pragmatic trials select outcomes that are meaningful to study participants. Our main outcome will be pain interference, or how pain interferes with a patient's daily life, an outcome identified as meaningful by our patient partners. This outcome is important because while we seek to prevent inappropriate overuse of opioids, the flip side – discontinuing appropriate use of opioids – should also be prevented. The net outcome – pain interference – reflects a balance between inappropriate overuse and underuse of effective pain treatments. Score = 5.
8. *Participant compliance with "prescribed" intervention.* Pragmatic trials measure little or no patient "compliance" with the intervention. When we administer the questionnaires, we will ask whether individuals have received and read the PEAT materials via REDCap but we will not measure adherence to or use of PEATs. Score = 4.
9. *Practitioner adherence to study protocol.* Trials with pragmatic designs use unobtrusive or no methods to measure practitioner adherence to the study protocol. We will measure when and for whom the CDS alerts are activated, but will not report feedback to providers. Score = 4.
10. *Analysis of primary outcome.* PRECIS notes that pragmatic trials include all enrolled patients in the final analysis and there is no separation of the intention-to-treat (ITT) vs. per protocol (PP) patients. We will conduct both ITT and PP analyses for sensitivity analysis purposes. We will ask patients whether they received and read the PEAT materials and will examine when the CDS alerts were fired and for which patients to conduct a PP analysis. Score = 3.

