E5.c. Power Calculations. Guided by previous work in chronic pain interventions,¹⁴⁰ we calculated sample size using an intracluster correlation coefficient of 0.02, an α level of 0.05, 90% power, and detection of a mean (SD) difference of 0.3 standard deviations on the PROMIS Pain Interference scale. We calculated a sample size of 320 patients per study arm, for a total of 640 patients. To compensate for predicted loss to follow-up, multiple variables in the final multi-level models, as well as sub-group analyses, we inflated the sample size by 50% to 960. Since we will be examining the effect of the interventions on a variety of sub-groups within the study sample, such as diagnoses of mental health conditions, race, ethnicity, gender, and chronic pain diagnosis, we will be adequately powered to detect meaningful differences. In our original proposal, we calculated a sample size of 320 patients per study arm for a total of 640 patients. To compensate for predicted loss to follow-up and non-response we had inflated the recruitment target size by 50% to 960. Under the current modification – and given the absence of changes to the assessment schedule, the estimated intracluster correlation coefficient, and the expected mean difference - the sample size required to adequately power the analysis remains unchanged. We believe the recruitment target will also remain consistent, and potentially even fall due to the ability of study staff to call passively enrolled patients and remind them to respond to assessments. We therefore anticipate being adequately powered to detect meaningful differences between the two arms.

E6 Heterogeneity of Treatment Effect (HT-1, HT-3, HT-4)

After reviewing the literature and consulting with our patient partners, we identified specific subgroups we plan to analyze to identify whether there is a heterogeneity of the treatment effects. Below we detail our planned sub-group analyses, our hypotheses, and our plans for statistical analysis for each subgroup. In order to address the problem of multiplicity, a Bonferroni correction will apply to all analyses.

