E7. Data Source Adequacy (IR-1). We plan to collect several types of data for this study. For the PROs, we will collect data directly from patients through web-based questionnaires. We will collect some data on comorbidities and medication use through data collected for clinical care and billing purposes through the EHR. Given that this data is not collected for research purposes, errors, particularly with regards to ICD-10 codes, are possible. We will work with our data warehouse to ensure that the data are cleaned prior to analysis and our statistical analysis team, led by [name], who has experience with clinical data collection and analysis,¹⁴¹ will also conduct extensive exploratory data analysis to identify potential errors in the data.

E7. Missing Data

a. Methods to Prevent and Monitor Missing Data. We anticipate two sources of missing data: the failure of patients to complete the initial set of questionnaires and the loss of patients to follow-up. Monitoring of missing questionnaire data will occur in real-time as online questionnaires are completed, completed partially, or never started. For enrolled patients who do not respond to the questionnaires after baseline, we will conduct two follow-up phone calls to attempt to collect data. After the intervention study period has ended, we will attempt one last follow-up phone call with a sub-sample of non-respondents to see if they are similar to respondents (MD-1). If so, for the hierarchical linear model, maximum likelihood estimation will be consistent as long as the data are missing at random (MD-3).¹³⁷ We are aware of the potential between failure to complete survey elements, failure to use the educational tools, and reduced HRQOL. These hypothesized patterns will receive close scrutiny in the analysis of the mechanisms.

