b. Statistical Methods to Handle Missing Data and Sensitivity Analyses. If the data is not missing at random, we will use multiple imputation techniques to impute missing data for respondents (MD-2). We plan on using the *mi impute mvn* command in Stata and will generate 20 datasets compatible with the regressions planned for the final analyses. To insure that the imputation has proceeded as expected, we will visually inspect parameters from successive iterations of the model to determine if they have reached a stationary distribution. We will conduct sensitivity analyses with the dataset that includes imputed data as well as with a dataset that does not include imputed data to determine the effect of the multiple imputation and plan on reporting both results. These precautions will serve to identify autocorrelation in the imputed data and allow for proper maintenance of uncertainty in imputed values (MD-3).

c. Reporting Reasons for Dropout and Missing Data. We will drop data from patients who do not have any visits with their PCP during the intervention period or are lost to follow-up, but will compare descriptive statistics for these patients to patients with at least one visit to their PCP for sensitivity analysis (MD-4, MD-5).

E9. Project Milestones and Timeline.

During the first 3-6 months of the study project, we will train the project staff, refine the study protocol, develop the data dictionaries, and obtain IRB approval. We will hold monthly meetings with our patient partners to finalize the study design and discuss issues related to IRB approval. In Year 1, Q4, we will passively enroll eligible patients in the two study arms. In the 4 weeks before the intervention period, we will send baseline questionnaires via REDCap. In Year 2, we will begin the intervention. We will conduct weekly reports from our EHR data warehouse to determine enrolled patient visits. Enrolled patients will be sent CG-CAHPS survey one day after each primary care visit. Enrolled patients will also receive the PROMIS questionnaires once a month. We will perform monthly checks to assess the completeness of data to minimize missing data and will complete one set of interim data analyses in Year 2 to assess whether there are any issues with missing data. Full data analysis will

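### The missing-data section drops patients who are lost to follow-up, a term the plan never defines; as written this discards PROMIS scores already collected, is not ITT, and undercuts the maximum-likelihood argument

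*Combined protocol and SAP*

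**What the plan says.** The rule is in E7 (Missing Data), part c: "We will drop data from patients who do not have any visits with their PCP during the intervention period or are lost to follow-up". Part c then offers only a comparison of descriptive statistics between the dropped patients and those with at least one PCP visit.

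Other places bear on it:

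- E7 (Missing Data), part a, names two sources of missing data: "the failure of patients to complete the initial set of questionnaires and the loss of patients to follow-up". Loss to follow-up is thus separate from never starting. No time window, number of missed surveys or event defines it.
- The same part says non-respondents will be sampled and compared with respondents and, if they are similar, "maximum likelihood estimation will be consistent as long as the data are missing at random".
- It also warns: "We are aware of the potential between failure to complete survey elements, failure to use the educational tools, and reduced HRQOL". The response is: "These hypothesized patterns will receive close scrutiny in the analysis of the mechanisms".
- E9 gives the collection schedule: a baseline questionnaire before the intervention, and then "Enrolled patients will also receive the PROMIS questionnaires once a month".
- Item 10 of the PRECIS list (analysis of primary outcome) says: "We will conduct both ITT and PP analyses for sensitivity analysis purposes". No section names the primary analysis set.
- D2 declares that patients without a PCP visit in the study period are excluded, and gives a reason: a stable population for the Aim 3 rates. It says nothing about loss to follow-up.

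**The concern.** Part c joins two groups with an *or*. The no-visit group is a declared population restriction and is not challenged here. The second group is defined by something that happens after randomisation, and its members will usually have scores on file. Three problems follow.

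1. Removing randomised patients because of a later event is not ITT, and the text is not reconciled with PRECIS item 10.
2. The consistency of maximum likelihood under missing at random depends on partial records staying in the likelihood. Part c removes them, so part a's justification no longer covers the analysis that would be run.
3. With the term undefined, the analysis set could be settled after data are seen.

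The arm comparison is biased if loss depends on outcome differently by arm. Part a links non-completion to not using the educational tools and to reduced HRQOL, and only the PEAT arm receives those tools (E4.c). The Executive Summary asks whether either strategy leaves patients with lower quality of life. A rule that can delete patients who did worse before leaving bears directly on that question.

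**Working it through.** **The plan's own figures (E5.c).** 320 per arm × 2 = 640, and 640 × 1.5 = 960. The plan explains: "To compensate for predicted loss to follow-up and non-response we had inflated the recruitment target size by 50% to 960". The largest whole-patient loss this absorbs is 1 − 640/960 = 320/960 = 33%. That is an upper limit for loss, because the allowance also covers non-response.

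**What is discarded.** Baseline plus 12 monthly PROMIS scores make 13 per patient. In the simulation below, lost patients had given 6 of 13 on average. At 33% loss the share thrown away is (320 × 6)/(320 × 6 + 640 × 13) = 1,920/10,240 = 19%.

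**Effect on the estimate.** The documents give no loss rates by arm, so every input here is assumed:

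- 480 patients per arm, 13 waves, no true effect;
- baseline variance 1, within-patient correlation 0.6;
- patients leave for good, with log-odds linear in the last observed score (missing at random);
- physician clustering not simulated; 800 trials per scenario; Monte Carlo SE 0.001-0.003.

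The growth slope is the arm difference in 12-month change, fitted by GLS with the true variance components. Each cell gives the false difference in SD units at 33% loss with lost patients dropped: growth slope / baseline-adjusted final wave. The final-wave contrast is not the planned model.

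| Log-odds of loss per SD (arm A, arm B) | Patient slope SD 0 | Patient slope SD 0.6 per year |
|---|---|---|
| 0.5, 0.5 | 0.000 / +0.001 | 0.000 / 0.000 |
| 0.4, 0.6 | 0.000 / −0.014 | −0.012 / −0.027 |
| 0, 0.5 | +0.003 / −0.044 | −0.027 / −0.077 |
| 0, 0.8 | +0.004 / −0.069 | −0.046 / −0.115 |

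Against the 0.3 SD design effect, 0.027/0.3 = 9% and 0.046/0.3 = 15%. A negative value favours the arm that lost its worse patients. With slope SD 0.3 and mechanism (0, 0.8), the growth-slope bias is about −0.01.

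**Other loss rates, growth slope, one arm only.**

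- Slope SD 0: 0.005 or less at both 15% and 50% loss.
- Slope SD 0.6: −0.009 to −0.019 at 15% loss, and −0.049 to −0.071 at 50%.

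**Precision (SE when dropping / SE when keeping).** 1.02-1.03 at 15% loss, 1.06-1.07 at 33% and 1.10-1.13 at 50%. Scores discarded are 8%, 19% and 31%.

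**Keeping every score.** The growth-slope bias is within 0.003 of zero in all 24 scenarios (four mechanisms, two slope SDs, three loss rates). A random-intercept-only model with all scores kept still shows −0.022 and −0.027 at slope SD 0.6 and 33% loss. Modelling patient slopes therefore matters.

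**Second set of assumptions (T-scores).** Intercept SD 8, slope SD 6 per year, residual SD 5, about 32-40% loss, arm-different mechanisms. Dropping gives −0.89 to −1.03 points; keeping all data gives 0.01 to 0.02. With a baseline SD of √(64 + 25) = 9.4, the bias is 0.09-0.11 SD. It exceeds the table's values partly because that fit holds both arms to one baseline mean, so baseline imbalance among the retained patients passes into the slope.

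**The case against.** **The sponsor may have meant only patients without visits.** Part c compares the dropped patients with those who had a visit. E4.c and E4.e speak of follow-up in terms of visits. Planning phone calls to patients who stop responding fits poorly with deleting them. This reading is possible, and under it few scores are at stake. But part c adds the second group with an *or*, and part a lists loss to follow-up on its own. The narrower meaning is not written.

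**The likelihood claim is conditional.** It applies only if sampled non-respondents resemble respondents; otherwise part b moves to multiple imputation and reports results both ways. That is correct, but imputation is described for respondents, and nothing says dropped patients return. If non-respondents are similar, dropping them still costs precision.

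**Loss that differs by arm is inferred.** Part a's warning names no arm. This stands: it is a plausible mechanism, not a documented one.

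**The bias figures depend on slope variation.** This also stands. At slope SD 0.2 the growth-slope bias was 0.000 even with one-arm-only loss. In the other direction, E4.d expects about 30% of 4,000 patients to complete every questionnaire. If lost meant not finishing, loss would be 70%, and the bias under mechanism (0, 0.8) is −0.107 SD with slope SD 0.6 and +0.008 with slope SD 0. Non-completion is not the same as loss, so this only shows how much hangs on the missing definition.

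**Part of the remedy is already there.** E5.b plans growth models with patient-level clustering and tests random effects. It does not commit to patient slopes.

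**Conclusion.** The concern holds: part c is wrong as written. Following it removes randomised patients with usable scores, conflicts with the ITT analysis in PRECIS item 10, and takes away the records on which part a's likelihood argument rests. Neither the descriptive comparison nor the imputation plan repairs this.

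The sure cost is precision, with an SE 6-7% wider at 33% loss. Bias in the planned growth model is about zero or small under most assumed mechanisms. It reaches 0.03-0.05 SD at 33% loss only when loss depends on outcome in one arm and patients' slopes vary widely; a model with a common baseline mean could show more. These sizes rest on assumed loss patterns, and actual size and direction cannot be found from the documents. Power is not the main issue, since 960 still leaves 640 after a one-third loss. This should be fixed before analysis; it does not invalidate the design.

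**What to change.** In E7 (Missing Data), part c:

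- Delete the loss-to-follow-up drop rule, and define the term for reporting only.
- State that the primary analysis includes all eligible patients by their physician's allocation, with every observed PROMIS and CG-CAHPS score kept in the likelihood-based models. Reconcile this with PRECIS item 10.
- Specify patient random intercepts and time slopes in the growth model.
- Report loss and visit attendance by arm.
- Keep the at-least-one-visit criterion of D2 as the declared population, and add a sensitivity analysis including no-visit patients who have data.

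If only patients without visits were ever meant, part c should say so.

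The cost is SAP wording and a little more analysis, with no new data, no larger sample and no change to the declared population. One limit remains: keeping all scores does not protect against loss that depends on unobserved scores.

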and dissemination research. CS-CORE's software and computer capabilities strengthen the team's ability to perform in-depth research. CS-CORE also has access to the main data and research facilities at Cedars-Sinai, including a staffed research library, a team of biostatisticians, experts in the fields of multiple specialties, and data analysts and programmers from the Enterprise Information Systems (EIS) work group, which manage all data for Cedars-Sinai. CS-CORE is located near the Medical Network, which will facilitate recruitment and study implementation.

G. Engagement Plan (PC-1). In accordance with PCORI's principles of Patient Engagement, this study includes patient engagement in all stages of the study, from the study design, outcomes selection, recruitment development, intervention implementation, data analysis and dissemination of results. All team members will have an equal voice in the process and all contributions will be valued. The Investigator team will communicate regularly with study partners via scheduled and unscheduled meetings and conference calls to elicit input from the stakeholders. Our primary Patient Partners, [name] and [name], will review study protocols, consent materials, and will contribute to manuscripts.

G1. Stakeholder Identification. We have initiated a number of collaborative partnerships with a wide range of stakeholders for this proposal, all of whom have important and distinct perspectives on chronic pain management. These groups include those receiving care for chronic pain, such as patients and individuals representing patient support groups; those providing care, such as clinicians and mental health professionals; and those that support the interaction between these two groups, such as consumer advocacy organizations.

1. Patient Partners: The ACPA has developed a variety of communication tools, including one of the communication tools used in this grant proposal, to assist patients in communicating their values and goals with their health care providers. [name] has presented the communication tools to dozens of Veterans Health Affairs organizations through the Veterans in Pain project and has also spoken to patients and health care system leaders about the importance of improving physician-patient communication.

2. Care Providers: Cedars-Sinai Medical Network (CS-MN): Part of the Cedar-Sinai Medical Center, the CS-MN serves 10,000 patients per month. PCPs represent one of the most important actors in the patient-physician chronic pain management interaction. **Pain Management Working Group:** The Working Group consists of a group of PCPs concerned with chronic pain management and opioid misuse. [name], who is the current head of the Working Group, will serve as the group's representative for this study.

3. Professional Organization: Consumer Reports: Consumer Reports Health works to create tools and educational materials aimed at supporting and empowering patients and facilitating interactions with their clinicians. The organization's priority is to ensure that patients and consumers have unbiased, clear information that can empower them in complicated decision-making processes. [name] and [name] will collaborate with the study investigators to represent Consumer Reports Health's voice in this study.

G2. Stakeholder Engagement. Phase 1: Planning the study. We began collaborating with our stakeholders even before the grant-writing process and their input and feedback has guided the development of our current study design. **Table 4** outlines the process through which our study design was developed in collaboration with our partners.

Phase 2: Conducting the Study. We will collaborate with our Patient Partners throughout the study planning and implementation phases to ensure that we develop patient-centered communications. We will hold monthly meetings prior to the study to develop protocols. During the data collection phase, we will monitor data collection for quality and completeness and will update our stakeholders to discuss issues that may arise.

At the conclusion of the implementation period, we will collaborate with our stakeholders during the statistical analyses to discuss the results. We will also create a Patient Advisory Board. We will invite patients who have previously participated in other chronic pain studies in our group to participate in a patient advisory board. They will receive information about the study via a newsletter and will be invited to make suggestions and changes throughout the study implementation period.

Phase 3: Disseminating the Study Results. We will collaborate with our stakeholders to disseminate the study results. Our Patient Partners will collaborate on the

development of manuscripts, presentations, and patient-facing materials – including a website that details the results of the study. We will work with the ACPA and Consumer Reports to create a communication strategy to disseminate the study through the lay media – a powerful opportunity for widespread dissemination. Additionally, the investigators will present the study findings alongside [name] and [name] at national and professional conferences.

C. Stakeholder Meetings. Regular, standing meetings will be held with stakeholder partners through all 3 years of the study. In order to facilitate participation, meetings will take place either in person or by phone. See Table 5.

Table 4. Stakeholder input in Study Design and Development	
Activities	Stakeholder Input
Outcome selection	
Patient Partner: [name]
 
 - Patient-provider communication suggested as primary outcome - Identified pain interference and overall health related quality of life as critical primary outcomes 
Patient Partner: American Chronic Pain Association
 
 - Suggested Patient-Reported Measures of communication/patient satisfaction as study outcomes
Research refinement	
Clinician Partner: Pain Management Working Group
 
 - Guided development of eligibility criteria based on understanding of high-risk patients
Study design	
Patient Partner: [name]
 
 - Provided guidance on instrument selection - Provided input on timing of the delivery of patient-facing education and activation materials 
Consumer Reports Health
 
 - Guided selection of education material 
Clinician Partner: Pain Management Working Group
 
 - Guided study design and protocol development

Meeting Schedule	Weekly	Monthly	Biannually
Year 1: Planning and patient recruitment	• Investigator Team, Pain Management Working Group	• Investigator Team, Patient Partners, Pain Management Working Group	• Investigator Team, Patient Partners, Consumer Reports, Pain Management Working Group
Year 2: Study Implementation	• Investigator Team, Pain Management Working Group	• Investigator Team, Patient Partners, Pain Management Working Group	• Investigator Team, Patient Partners, Consumer Reports, Pain Management Working Group

